3.2 COHORT 2 STUDY TREATMENT

The study period of cohort 2 subjects comprises a Baseline period (6 weeks), a T+M period (15 weeks: (21 days for dose titration + 12 weeks maintenance), a Taper period or transition period, and a Post Dosing visit after study completion or early termination.

Upon completion of the Baseline Period, subjects who qualify for the study will be randomized (1:1) in a double-blind manner to receive ZX008 (0.5 mg/kg/day, 20 mg/day maximum) or placebo. Randomization will be stratified by age group (<6 years, \geq 6 years) to ensure balance across treatment arms, and initially it was hoped that at least 40% of subjects will be in each age group. The actual % of subjects in each stratum may be different from this goal. Subjects will be assigned a randomization number by the IVR/IWR system upon confirmation that the subject qualifies for enrollment in the Titration Period. All subjects will be titrated to their randomized dose during the Titration Period. Titration will occur in 3 steps starting with a 0.2 mg/kg/day dose of ZX008 (or placebo equivalent) on Study Days 1-7, increased to a dose of 0.4 mg/kg/day on Study Day 8-14, and then increased to a dose of 0.5 mg/kg/day on Study Days 15-21; the maximum daily dose at any point is 20 mg/day. The duration of the titration period will be 21 days.

There will be cardiac safety follow-up of 3 to 24 months after study drug discontinuation for early termination or for subjects who complete the study but do not enroll in the open-label extension study. These results will be presented elsewhere.

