6.3.1.1 Primary Analysis Tests

T + M Period:

The primary analysis will compare the ZX008 0.5 mg/kg/day group to the placebo group using a two-sided test at $\alpha = 0.05$ level of significance.

The primary endpoint (CSF_{T+M}) will be analyzed using an analysis of covariance (ANCOVA) model with treatment group (ZX008 or Placebo) and age group (< 6 years, ≥ 6 years) as

classification factors, log baseline frequency (CSF_B) as a covariate in the model, and log CSF_{T+M} as response. Treatment group means and the difference from placebo will be estimated with least squares means from the analysis model along with 95% confidence intervals and associated 2-sided p-values. Estimated treatment group means and CI endpoints will be exponentiated for presentation.

The null hypothesis

$$H_0: \mu_{Z008} - \mu_P = 0,$$

will be tested against the alternative

$$H_A: \mu_{Z008} - \mu_P \neq 0,$$

where μ_{Z008} and μ_P represent the ZX008 0.5 mg/kg and Placebo group means (on the log scale), respectively.

Rejection of the null hypothesis in favor of the alternative, in the presence of a statistically significantly bigger reduction in mean convulsive seizure frequency from baseline for the treatment group compared to the placebo group, (two-sided p-value < 0.05) will be regarded as evidence of a treatment benefit in favor of ZX008 0.5 mg/kg group.

Sample SAS code for the ANCOVA described above is as follows:

```
proc glm data=temp;
  class agegrp trtp;
  model csftm = bcsf agegrp trtp / SS3;
  lsmeans trtp / pdiff stderr;
```

where trtp = randomized treatment group (with codes 1, 2 indicating placebo, and 0.5 mg groups).

bcsf = log(CSF_B),
csftm = log(CSF_{T+M})
agegrp = age group.

Additional statements may be used to obtain estimates and 95% confidence interval. Endpoints of the CIs may be exponentiated to obtain CI on the original scale. Fitted values and residuals may be plotted to check model assumptions.

Since the ANCOVA used in the primary analysis relies on assumptions of normality, the primary endpoint will also be analyzed using a nonparametric method that does not require as stringent assumptions. A nonparametric ANCOVA will be used to analyze the data, with ranks of the baseline CSF_B as a covariate and ranks of CSF_{T+M} as response. If normality assumptions are not met, the results of the nonparametric test will be used to assess the primary objective.

Treatment by Baseline Seizure Category:

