6.3.3.6 Incidence of Rescue Medication Usage

Use of rescue medication is recorded on the daily diary. In the event of prolonged seizures or status epilepticus, rescue medication is administered according to each subject's personalized regimen consisting of one or more medications. If the first rescue administration does not control the seizures, a second or even third round might be administered. The second and third round might use medications or doses different from the first round of rescue meds.

Rescue medication will be summarized by treatment group and by active treatment vs. Placebo for the following:

- The number of days rescue medication was taken (normalized to 28 days) will be summarized for the T + M period by the mean, standard deviation (SD), median and range. The ZX008 treatment group will be compared to the placebo group using a rank ANCOVA analogous to that described in [Section 6.3.1.1](#). Specifically, the ANCOVA will use ranks of rescue medication frequency during T+M as the response, and will incorporate treatment group as a classification factor and the ranks of rescue medication frequency during Baseline as a covariate.

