In addition, the change from baseline in each QOLCE subscale score will be calculated for each subject by subtracting the baseline score from the score measured at End of Study/ET. The change from baseline for each treatment group will be summarized by the mean (SD) and treatment groups will be compared using a Wilcoxon test.

Individual subject data for the domains will be listed.

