6.3.3.11 Pediatric Quality of Life Inventory (PedsQL 4.0 Generic Core) Scale

The PedsQL 4.0 is a quality of life scale that measures four functional areas (physical, emotional, social, and school functioning). The scale is available in age-appropriate instruments with child self-report and parent proxy-report formats. In this study, the age appropriate categories for the administration of the instrument were ages 2-4, 5-7, 8-12 and 13-18 years, and the Parent Reports were used.

There are 8 items for Physical Functioning, and 5 questions each for Emotional, Social, and School Functioning. Each of the responses to the 23 items is initially scored on a 5 point Likert scale from 0 (Never) to 4 (Almost always). Scores will be linearly transformed to a scale of 0 to 100, where 0=100, 1=75, 2=50, 3=25 and 4=0, and higher scores mean better health related

quality of life. If more than 50% of the items in the scale are missing, the scale scores should not be computed. A mean score is calculated as the sum of the items over the number of items answered. If some of the answers on a scale are missing but 50% or more of the items in the scale are completed, then impute the mean of the completed items in a scale. The scaled results will be combined across age categories to produce a single score for each functional area.

A Psychosocial Health Summary score is computed as the sum of the items over the number of items answered in the Emotional, Social, and School Functioning Scales.

A Physical Health Summary score is made up of the Physical Functioning Scale Score.

The Total Score is computed as the sum of all the items over the number of items answered on all the Scales.

Descriptive statistics at both Baseline and EOS/ET will be provided for the Psychosocial Health Summary score, the Physical Health Summary score and Total Score.

The change from baseline for the Total Score will be calculated for each subject by subtracting the Total Score measured at Baseline from the Total Score measured at End of Study/ET. The change from baseline will be summarized with descriptive statistics and treatment groups will be compared on the Total Score using a Wilcoxon test.

The next two ratings evaluate the change from baseline in the responsible parent/caregiver's quality of life during the time the subject is in the trial:

6.3.3.12 Change from Baseline in the Quality of Life of the Parent/Caregiver using EQ-5D-5L Scale

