The impact on the quality of life of the parent/caregiver responsible for a patient with DS will be assessed at Baseline (Visit 3) and at End of study (Visit 12) using the EQ-5D-5L.

The EQ-5D-5L health questionnaire is a health-related quality of life instrument with 5 dimensions: mobility, self-care, usual activities, pain/discomfort, and anxiety/depression. Each dimension has 5 possible levels: no problems, slight problems, moderate problems, severe problems and extreme problems.

The summary of results will follow the EQ-5D-5L guideline results presentation. For the "Health Profiles" descriptive system summary results will show the number, and proportion (%) of subjects in each Item score (No Problems, Slight Problems, Moderate Problem, Severe Problem, Extreme Problems) by treatment at baseline and at the end of study. In addition, the item scores will be classified into two categories as "No Problems" and "Problems", the latter comprised of moderate, severe and extreme problems. Summary results will show number of patients and proportion (%) with "No Problems" and with "Problems" by treatment at baseline and at end of study time point.

For the VAS measure of overall self-rated health status, descriptive statistics summary results will be presented for the VAS score showing number of subjects, mean, standard deviation, median, and range by each treatment at baseline and end of study time points.

The change from baseline in VAS will be calculated by subtracting the VAS score at baseline from the VAS score obtained at End of Study/ET. The change in VAS will be summarized using descriptive statistics, and treatment groups will be compared using a Wilcoxon test.

The quality of life of parent/caregiver individual data will be listed using EQ-5D-5L scale.

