6.3.3.13 Pediatric Quality of Life Inventory (PedsQL 2.0 Family Impact Module) Scale

The PedsQL™ Family Impact Module was designed to measure the impact of pediatric chronic health conditions on parents and the family. The PedsQL™ Family Impact Module measures parent self-reported physical, emotional, social, and cognitive functioning, communication, and worry. The Module also measures parent-reported family daily activities and family relationships.

There are 6 items for Physical Functioning, 5 items each for Emotional Functioning, Cognitive Functioning and Worry, 4 for Social Functioning, and 3 for Communication. There are additionally 3 questions for Daily Activities and 5 for Family Relationships.

Each of the responses to the 36 items is initially scored on a 5 point Likert scale from 0(Never) to 4 (Almost always). Scores will be linearly transformed to a scale of 0 to 100, where 0=100, 1=75, 2=50, 3=25 and 4=0, and higher scores mean better health related quality of life. If more than 50% of the items in the scale are missing, the scale scores should not be computed. A mean score is calculated as the sum of the items over the number of items answered. If some of the answers on a scale are missing but 50% or more of the items in the scale are completed, then impute the mean of the completed items in a scale.

The Parent HRQL Summary Score (20 items) is computed as the sum of the items divided by the number of items answered in the Physical, Emotional, Social, and Cognitive Functioning scales.

The Family Functioning Summary Score (8 items) is computed as the sum of the items divided by the number of items answered in the Daily Activities and Family Relationships scales.

The Total Score is the sum of all 36 items divided by the number of items answered.

Descriptive statistics for baseline and EOS/ET will be provided for the summary scores. The change from baseline will be calculated and ZX008 and placebo groups will be compared using the same methods as specified for the PedsQL 4.0 analysis.

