6.4.11 Brief Rating Inventory of Executive Function (BRIEF)

The Behavior Rating Inventory of Executive Function (BRIEF™) and its preschool version, BRIEF-P, are standardized, validated rating scales to measure executive function in children within the home and school environments that will be assessed by the parent according to the schedule in [Table 1](#) (i.e. at Randomization (Visit 3), at Maintenance period (Visit 8) and at End of study visit (Visit 12)).

The BRIEF measures multiple aspects of executive functioning; scales include Inhibit, Shift, Emotional Control, Initiate, Working Memory, Plan/Organize, Organization of Materials and Monitor.

The original BRIEF was the basis for the development of the BRIEF-P. The BRIEF-P Rating Form consists of 63 items that measure various aspects of executive functioning: Inhibit, Shift, Emotional Control, Working Memory, and Plan/Organize.

For the BRIEF and the BRIEF-P, mean scores at Baseline, End of Study/ET and mean change from baseline to End of Study/ET, and descriptive statistics will be presented by treatment group for the Safety population (SAF). The change from baseline in the ZX008 and placebo groups will be compared using Wilcoxon tests.

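### The quality-of-life and BRIEF scales are compared by unstratified Wilcoxon tests on change from baseline, a valid choice that uses the collected baseline only by subtraction and probably gives up some precision

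*SAP*

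**What the plan says.** Five sections of the SAP specify the same kind of comparison.

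- QOLCE subscales (6.3.3.10): "The change from baseline for each treatment group will be summarized by the mean (SD) and treatment groups will be compared using a Wilcoxon test".
- PedsQL 4.0 (6.3.3.11), on change in the total: "treatment groups will be compared on the Total Score using a Wilcoxon test".
- Caregiver EQ-5D-5L (6.3.3.12): "The change in VAS will be summarized using descriptive statistics, and treatment groups will be compared using a Wilcoxon test".
- PedsQL Family Impact (6.3.3.13): "ZX008 and placebo groups will be compared using the same methods as specified for the PedsQL 4.0 analysis", which makes it a Wilcoxon test on change.
- BRIEF and BRIEF-P (6.4.11): "The change from baseline in the ZX008 and placebo groups will be compared using Wilcoxon tests".

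None of these sections names a baseline covariate, the age stratum, or an estimate of the treatment difference with a confidence interval. Baseline scores are collected at Visit 3. SAP 3.2 says of the design: "Randomization will be stratified by age group", with the cut at 6 years.

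Elsewhere the SAP adjusts. For the primary endpoint (6.3.1.1): "The primary endpoint (CSF_{T+M}) will be analyzed using an analysis of covariance (ANCOVA) model", with age group as a factor and log baseline as covariate. Seizure-free days (6.3.3.1) take their own baseline as covariate. Non-convulsive seizures (6.3.3.3) use a rank ANCOVA with ranked baseline. So does rescue medication (6.3.3.6), where "the ANCOVA will use ranks of rescue medication frequency during T+M as the response" is paired with the baseline ranks. CGI-I (6.3.3.14) and the status epilepticus composite (6.3.3.8) use Cochran-Mantel-Haenszel tests stratified by age group. The SAP gives no reason for treating the questionnaires differently.

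**The concern.** Subtracting baseline amounts to fixing its slope at 1. When the correlation between baseline and end of study is below 1 and the variances are similar, the best slope is smaller, and the subtraction carries baseline noise into the comparison. ANCOVA estimates the slope and removes that noise at no cost in data. Leaving out the stratification factor loses a little more wherever age predicts the score.

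At stake is precision on four additional secondary objectives (SAP 2.3) and on the scale that SAP 2.4 names for cognitive function. For these scales the Wilcoxon tests are the only between-group tests planned. For BRIEF, a wider margin of uncertainty makes a cognitive effect in either direction harder to see, and a p-value alone does not show how large a harm has been excluded.

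**Working it through.** **The plan's own power figures.** They concern the primary endpoint only. n per arm = 2(1.960 + 1.282)² × (SD/difference)².
- Protocol 10.1: SD 58, difference 40 gives 2 × 10.51 × 2.1025 = 44.2, so 45 per arm. Power is 0.905 (0.899 from the t distribution).
- SAP 6.1.10: SD 55, difference 40 gives 2 × 10.51 × 1.8906 = 39.7, so 40 per arm. Power is 0.902 (0.895 from t).

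Both reproduce. Neither document gives a power or precision figure, or a baseline-to-end correlation, for any of the scales discussed here.

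**Variance of the two approaches.** Assume equal variance σ² at baseline and end of study, with correlation r.
- Change score: variance proportional to 2(1 − r)σ².
- ANCOVA on baseline: (1 − r²)σ² = (1 − r)(1 + r)σ².
- Ratio, change to ANCOVA: 2(1 − r)/[(1 − r)(1 + r)] = 2/(1 + r).
- ANCOVA saving: 1 − (1 + r)/2. Equivalent n for 45 per arm: 45(1 + r)/2.

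**Power with the planned test.** The ratio describes comparisons of means, so the Wilcoxon test itself was simulated: 3,000 runs per setting, 45 per arm, 40% under 6 years, normal data. The treatment difference was set so that a comparison of mean change has about 80% power. ANCOVA includes baseline and age group. The correlation and the age effect are assumptions.

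| r | 2/(1+r) | variance saved | n doing the work of 45 | Wilcoxon vs ANCOVA, no age effect | Wilcoxon vs ANCOVA, age effect 0.5 SD |
|---|---|---|---|---|---|
| 0.3 | 1.54 | 35% | 29 | 0.78 vs 0.93 | 0.77 vs 0.93 |
| 0.5 | 1.33 | 25% | 34 | 0.76 vs 0.88 | 0.75 vs 0.89 |
| 0.7 | 1.18 | 15% | 38 | 0.78 vs 0.85 | 0.75 vs 0.86 |
| 0.9 | 1.05 | 5% | 43 | 0.76 vs 0.79 | 0.67 vs 0.81 |

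**Validity.** With no treatment effect (r = 0.7, age effect 0.5 SD), the Wilcoxon test rejected in 3.7% of runs, below the nominal 5%.

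**Where age group can be used.** Protocol 7.3.5 gives BRIEF-P to children under 5 at baseline, and SAP 6.9 says ages 2 to 4. All of them fall in the under-6 stratum, so the factor is constant and cannot be estimated. BRIEF covers ages 5 to 18, so only five-year-olds are in the younger stratum. The age point therefore bears on QOLCE, PedsQL and the caregiver scales. It is most plausible for PedsQL, which combines four age-specific forms into one score. Whether the child's age predicts a caregiver's EQ VAS or Family Impact score is unknown.

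**The case against.** The strongest case for the plan is that a distribution-free test is a defensible choice for bounded questionnaire scores, and that ANCOVA does not always win. This stands. With heavy-tailed errors (t with 3 degrees of freedom) and no age effect, the Wilcoxon test on change beat parametric ANCOVA at r = 0.7 (0.92 vs 0.87) and at r = 0.9 (0.94 vs 0.83). Rank ANCOVA with baseline and age did slightly better than Wilcoxon at 0.7 (0.94 vs 0.92) but worse at 0.9 (0.83 vs 0.94). On the other side, a separate simulation with scores confined to 0–100 favoured ANCOVA throughout: 0.75 vs 0.91, 0.79 vs 0.91, 0.85 vs 0.89 and 0.84 vs 0.88 at r = 0.3, 0.5, 0.7 and 0.9. The case for ANCOVA as the main comparison is good but conditional, which is why the Wilcoxon test is worth keeping.

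A second objection is that 45 per arm flatters these scales. That is right too. The SAP plans 40. BRIEF and BRIEF-P split the sample. Family Impact is not assessed in the Netherlands, and caregiver scales are skipped without consent or when the usual caregiver is absent (Protocol 7.1 and 7.1.7). The variance ratio does not depend on n, but the power figures do.

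A third is that the SAP's rank ANCOVA is no precedent for an age term. As written in 6.3.1.1, 6.3.3.3 and 6.3.3.6 it names ranked baseline and no age factor. The precedents for age are the primary ANCOVA and the Cochran-Mantel-Haenszel tests.

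A reader might also infer that regression to the mean biases these comparisons. The documents do not support that. Under randomisation the change-score comparison is unbiased on average, and a distortion arises only conditionally, when the arms happen to differ at baseline.

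**Conclusion.** The point holds as a modest question of efficiency. For five sets of scales the plan uses the baseline less fully than it does for its seizure-frequency and rescue-medication endpoints. If variances are equal, the change score has 1.54 to 1.05 times the ANCOVA variance over r from 0.3 to 0.9. The documents do not fix r, and at high r, or with heavy tails, the gain shrinks or reverses. The age term adds something only where age predicts the score. It is unavailable for BRIEF-P and close to empty for BRIEF.

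Two further inferences go beyond the documents. First, these are not the only analyses of the scales: the SAP also summarises EQ-5D-5L profiles, PedsQL summary scores and BRIEF means, and the QOLCE cognition subscales bear on cognition as well. They are the only between-group tests of these scales. Second, nothing here touches the trial's main result. SAP 6.1.2 confines formal testing to the primary and two key secondary endpoints, so those conclusions are unaffected.

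**What to change.** Before unblinding, amend SAP 6.3.3.10 to 6.3.3.13 and 6.4.11 as follows.

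- Make the between-group comparison an ANCOVA of the End of Study/ET score on treatment and the same scale's baseline.
- Add age group (under 6, 6 and over) for QOLCE, PedsQL, Family Impact and EQ VAS. Omit it for BRIEF-P. For BRIEF it is optional.
- Report the adjusted treatment difference with its 95% CI.
- Keep the Wilcoxon test on change, or the SAP's rank ANCOVA, as a prespecified sensitivity analysis for skewed or heavy-tailed scores.
- Keep the descriptive change scores as planned.

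The cost is SAP wording and one extra model per score analysed, with no new data. The downside is a possible loss of power against the Wilcoxon test if errors are heavy-tailed and r is high. The retained sensitivity analysis would show whether the choice matters.

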6.3.3.11 Pediatric Quality of Life Inventory (PedsQL 4.0 Generic Core) Scale

The PedsQL 4.0 is a quality of life scale that measures four functional areas (physical, emotional, social, and school functioning). The scale is available in age-appropriate instruments with child self-report and parent proxy-report formats. In this study, the age appropriate categories for the administration of the instrument were ages 2-4, 5-7, 8-12 and 13-18 years, and the Parent Reports were used.

There are 8 items for Physical Functioning, and 5 questions each for Emotional, Social, and School Functioning. Each of the responses to the 23 items is initially scored on a 5 point Likert scale from 0 (Never) to 4 (Almost always). Scores will be linearly transformed to a scale of 0 to 100, where 0=100, 1=75, 2=50, 3=25 and 4=0, and higher scores mean better health related

quality of life. If more than 50% of the items in the scale are missing, the scale scores should not be computed. A mean score is calculated as the sum of the items over the number of items answered. If some of the answers on a scale are missing but 50% or more of the items in the scale are completed, then impute the mean of the completed items in a scale. The scaled results will be combined across age categories to produce a single score for each functional area.

A Psychosocial Health Summary score is computed as the sum of the items over the number of items answered in the Emotional, Social, and School Functioning Scales.

A Physical Health Summary score is made up of the Physical Functioning Scale Score.

The Total Score is computed as the sum of all the items over the number of items answered on all the Scales.

Descriptive statistics at both Baseline and EOS/ET will be provided for the Psychosocial Health Summary score, the Physical Health Summary score and Total Score.

The change from baseline for the Total Score will be calculated for each subject by subtracting the Total Score measured at Baseline from the Total Score measured at End of Study/ET. The change from baseline will be summarized with descriptive statistics and treatment groups will be compared on the Total Score using a Wilcoxon test.

The next two ratings evaluate the change from baseline in the responsible parent/caregiver's quality of life during the time the subject is in the trial:

6.3.3.12 Change from Baseline in the Quality of Life of the Parent/Caregiver using EQ-5D-5L Scale

The impact on the quality of life of the parent/caregiver responsible for a patient with DS will be assessed at Baseline (Visit 3) and at End of study (Visit 12) using the EQ-5D-5L.

The EQ-5D-5L health questionnaire is a health-related quality of life instrument with 5 dimensions: mobility, self-care, usual activities, pain/discomfort, and anxiety/depression. Each dimension has 5 possible levels: no problems, slight problems, moderate problems, severe problems and extreme problems.

The summary of results will follow the EQ-5D-5L guideline results presentation. For the "Health Profiles" descriptive system summary results will show the number, and proportion (%) of subjects in each Item score (No Problems, Slight Problems, Moderate Problem, Severe Problem, Extreme Problems) by treatment at baseline and at the end of study. In addition, the item scores will be classified into two categories as "No Problems" and "Problems", the latter comprised of moderate, severe and extreme problems. Summary results will show number of patients and proportion (%) with "No Problems" and with "Problems" by treatment at baseline and at end of study time point.

For the VAS measure of overall self-rated health status, descriptive statistics summary results will be presented for the VAS score showing number of subjects, mean, standard deviation, median, and range by each treatment at baseline and end of study time points.

The change from baseline in VAS will be calculated by subtracting the VAS score at baseline from the VAS score obtained at End of Study/ET. The change in VAS will be summarized using descriptive statistics, and treatment groups will be compared using a Wilcoxon test.

The quality of life of parent/caregiver individual data will be listed using EQ-5D-5L scale.

